### **BACKGROUND**

The burden of burns and pain. Burn injuries are among the leading causes of visits to the emergency department and hospitalizations in young children. They mostly result from scalds and contact with household appliances. Regardless the cause of the injury, dressing changes and hydrotherapy sessions for burn injuries are associated with extreme pain. The management of acute pain experienced during hydrotherapy sessions in patients with burn injuries, called procedural pain, remains a major challenge for healthcare professionals. Pain can have several short term effects on the child on the development, mood, sleep, appetite, school performance, anxiety and distress levels. In the long term, it can decrease the pain threshold, cause stress disorders, affect social behavior and seeking of medical services. In burn injuries, pain is often accompanied by great anxiety, which in turn, decreases pain tolerance. To relieve pain and anxiety, clinicians usually rely on pharmacological agents via the administration of high doses of opioids and anxiolytics. The use of these medications can cause deep sedation in children, and many side effects such as nausea, vomiting, and respiratory depression. Also, despite the growing use of opioids, patients report pain of more than 7 on a scale of 0-10 during their dressing changes and hydrotherapy sessions. Multimodal approaches combining medication and non-pharmacological interventions should be explored to reduce pain and anxiety associated with painful procedures.

Innovation of non-pharmacological pain interventions. Studies and reviews have highlighted, in recent years, the effectiveness of multimodal approaches combining medication with non-pharmacological interventions for procedural pain relief. Distraction techniques have been recognized among the most effective non-pharmacological interventions. They divert the child's attention to an attractive element, hindering the perception of the painful stimuli and therefore reducing pain and anxiety. Distraction is based on the gate control theory of Melzack and Wall stating a link between perception of pain and level of attention devoted to the stimulus affecting the painful experience. Therefore, distraction techniques engaging multiple senses such as vision and audition may grab the child's attention more than the techniques that only engage one sense. Hence, the increasing interest in more immersive and interactive methods of distraction such as virtual reality (VR) for the management of procedural pain.

Virtual reality distraction. This is an active distraction method that allows the user to interact with an immersive environment generated by a computer stimulating different senses (vision,

hearing and sometimes touch). VR allows a mental escape through multisensory interaction. Its effect is known to decrease pain and anxiety. In the past ten years, VR was tested through different studies with older children and adult burn victims. A study by Hoffman et al. in 2007, showed that the percentage of reduction in pain by VR was comparable to the reduction resulting from a moderate dose of hydromorphone equivalent to what a patient would receive during a burn wound care. Yet, the authors state that they believe the best analgesia is achieved by combining VR with pharmacological treatment. However, very few studies have tested the effect of a combination of pharmacological and virtual reality interventions, on procedural pain and anxiety of young children suffering from burn injuries. Also, current studies on VR mostly use 3D goggles or helmets in contact or close to the face of the child which could be challenging with young children since they mostly have burns on their face and upper trunk. Therefore, a new VR prototype has been developed in collaboration with the Society of Arts and Technology (SAT) in Montreal to provide an immersive interactive experience for the burn child in the hydrotherapy tank. The prototype was developed after several meetings between the researchers, the designers and engineers and the surgical-trauma team of CHU St. Justine. Meetings were followed by an ergonomic study of the hydrotherapy room to meet the unit's and patients' specifications and ensure that it doesn't interfere with the healthcare professionals work.

## **AIM**

The aim of this pilot study is to assess the feasibility and applicability of the prototype as well as the satisfaction of the healthcare professionals regarding the use of the VR prototype for the relief of procedural pain and anxiety in young children with burn injuries.

Primary Research Question: In children from 2 months to 10 years old who have suffered burn injuries, is VR distraction a feasible, applicable and satisfactory method for pain relief during hydrotherapy? Secondary Research Question: In children from 2 months to 10 years old who have suffered burn injuries, does VR distraction provide better pain and anxiety relief during hydrotherapy than standard pharmacological treatment?

## **HYPOTHESES**

- a. VR distraction is a feasible and acceptable non-pharmacological method for procedural pain relief (during hydrotherapy) of young children with burn injuries.
- b. VR distraction combined with analgesics is more efficacious than standard treatment (analgesics alone) on procedural pain and anxiety (during hydrotherapy) of young children with burn injuries.

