## **METHODS**

**Design**. Single-arm pilot study.

**Sample and Setting**. Participants will be recruited through convenience sampling upon admission to the surgical-trauma burn unit. The unit has a hydrotherapy room for inpatients and outpatients. Healthcare professionals usually present during hydrotherapy are: a burn wound care nurse, a nurse clinician from the pain clinic, an anesthetist, a physical therapist and an orderly. The size of the total desired sample is 15 to 20 participants depending on the recruitment rate since it is a pilot study. The study will take place in the hydrotherapy room of the CHU St. Justine, a large pediatric university teaching hospital in Montreal where the VR prototype is installed.

Eligibility criteria. Inclusion criteria: children from 2 months to 10 years old, with a burn injury, requiring a hydrotherapy session for burn wound care, and accompanied by a consenting parent/legal tutor who can understand, read, and write either French or English. Exclusion criteria: 1) Admitted to the intensive care Unit, 2) Neuro-cognitive disability that precludes children from interacting with the distraction intervention, 3) Unconscious or intubated during hydrotherapy session, 4) Suffering from epilepsy (considering the nature of the intervention), 5) Allergic to opioids or other analgesics used for standard pharmacological treatment.

**Intervention**: The child will visualize and interact with the virtual environment throughout the hydrotherapy session. VR prototype developed by the SAT will be used as the experimental intervention. It has a wide screen installed at the end of the hydrotherapy tank offering a 150-degree field view, on which appears a game allowing the child to have the immersive entertainment experience without the need to wear a helmet or 3D glasses. The child or a proxy, depending on age and burn site, will have the opportunity to interact with the game. The interactive component is not mandatory for the immersive and distractive experiences provided by the prototype. Video

games tailored to the child's age and injury, different from the commercially available ones, will be adapted to each age-group of children recruited with control over the speed of movement to avoid motion sickness.

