**Measures**. Measures of baseline pain and anxiety will be recorded at T1, 30 minutes before the procedure, in the patient's room. Measures for procedural pain, anxiety and sedation level will be taken at: T2, before the procedure, upon arrival in the hydrotherapy room, T3, during the procedure (10 min after the beginning of the hydrotherapy session), T4, immediately after the procedure before leaving the hydrotherapy room and T5, 30 minutes after the procedure in the patient's room. The patient's comfort level will also be assessed during the procedure at T3. Finally, the acceptability of the intervention will be assessed through a questionnaire comprising items on the acceptability and satisfaction of the healthcare professionals at T4. The same measures will be recorded for each participant for up to three hydrotherapy sessions. The primary outcome will be the acceptability of the intervention. Comparisons will be made between pain and anxiety levels for the same order of session.

**A) Primary Outcome Measure**: Acceptability [Time Frame: T4, immediately after the procedure before leaving the hydrotherapy room]: To assess the acceptability including the satisfaction of healthcare professionals regarding the use of the VR prototype during the hydrotherapy session. Pre-tested tailored questionnaire including satisfaction and acceptability outcomes (tolerance, positive and negative aspects, secondary effects).

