### CONTRIBUTION AND EXPECTED RESULTS

Despite growing interest in the field, procedural pain management in children remains suboptimal and the importance of developing more effective methods is required. This project will provide

preliminary evidence on the feasibility, acceptability, and preliminary efficacy of non-pharmacological methods of procedural pain management through the development and testing of innovative interventions. VR distraction could be an interesting method to relieve pain, easy to use and without known side effects. The investigators hope that it could reduce the need for opioids and anxiolytics in burn children and decrease the pain related to the procedures while providing a less traumatizing hospital experience, which is often the first for children under 5 years old. The expected results have a direct effect on physical (pain, comfort) and psychological (anxiety) health of the child. In addition, clinical implications may include other indicators of quality of care and economic benefits such as duration of the hydrotherapy session, the amount of opioids and anxiety drugs administered, the use of coanalgesics, the number of professionals required in the hydrotherapy room and duration of wound healing.

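### Hypothesis b sets VR plus analgesics against analgesics alone, but the single-arm plan names no analgesics-alone data, so the comparison cannot be made

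*Combined protocol and SAP*

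**What the plan says.** Two places set a comparative objective. Hypothesis b reads: "VR distraction combined with analgesics is more efficacious than standard treatment (analgesics alone) on procedural pain and anxiety". The secondary question in the Aim asks: "does VR distraction provide better pain and anxiety relief during hydrotherapy than standard pharmacological treatment". Only hypothesis b says that VR is combined with analgesics. The secondary question names VR distraction and leaves the combination unstated.

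The Methods describe a different kind of study. The design is a "Single-arm pilot study" of 15 to 20 children. Under Intervention: "The child will visualize and interact with the virtual environment throughout the hydrotherapy session". Under Measures: "The same measures will be recorded for each participant for up to three hydrotherapy sessions". The same paragraph adds: "Comparisons will be made between pain and anxiety levels for the same order of session". It does not say between whom.

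The Data Analysis Plan gives non-parametric comparisons of pain, anxiety and sedation before, during and after the procedure. It adds a comparison of the proportion of patients given rescue medication and a chi-square test for dichotomous variables. It names no groups for either.

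The Contribution and Expected Results section promises "preliminary evidence on the feasibility, acceptability, and preliminary efficacy of non-pharmacological methods of procedural pain management".

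**The concern.** A claim that one treatment is better than another needs observations under both. Here the objective is comparative, while the design and analysis describe one condition only. The Data Analysis Plan nevertheless contains inferential tests. A significant change in FLACC between arrival and the tenth minute, or between the tenth minute and the end, could be reported next to hypothesis b as support for it. The commitment to preliminary efficacy in the Contribution section makes that reading easy. What is at stake is what the pilot may conclude about efficacy and what planners of the larger trial take from it.

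**Working it through.** The plan gives no power calculation, effect size or SD for this comparison, so there is no stated figure to reproduce. The check is whether any part of the plan supplies data on hydrotherapy with analgesics alone.

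**Candidates for the missing comparator**

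- *A concurrent group.* None: the design is single-arm.
- *Sessions without VR in the same child.* None is described. Up to three sessions carry the same measures, and no session is assigned to a non-VR condition.
- *Time points outside the procedure.* T1 and T2 precede hydrotherapy and T5 follows it by 30 minutes. These are not observations of hydrotherapy without VR. Comparing them with T3 changes the procedure and the VR exposure together.
- *The session-order comparison in Measures.* It could imply a second cohort, but no cohort is named.
- *The rescue-medication comparison and the chi-square test.* Both need at least two groups or conditions, and the plan identifies none.
- *The Background figure.* It says that "patients report pain of more than 7 on a scale of 0-10 during their dressing changes and hydrotherapy sessions". This is a patient-reported statement with no ages, sample size or SD. It is not given on FLACC and is not linked to any analysis.

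The number of analgesics-alone observations that the plan provides is therefore zero.

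**Why the within-session change cannot stand in**

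Write the mean change from T2 to T3 under the study as

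observed change = C + V,

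where C is the change that the procedure, analgesia and time would produce without VR, and V is the effect of VR. Hypothesis b concerns V. The study observes only the sum C + V. Suppose, purely for illustration, that mean FLACC rises by 2:

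- C = +2 and V = 0 gives 2 + 0 = 2 (VR does nothing);
- C = +3 and V = -1 gives 3 - 1 = 2 (VR lowers pain by one point).

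The data are identical in the two cases. More children would estimate the sum more precisely but would not separate C from V. The same holds for anxiety and sedation. It also holds for rescue use, where a single-group proportion has nothing to be set against.

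**The case against.** The strongest reply is that this is a pilot. A single arm is a legitimate choice, acceptability is the primary outcome, and the Contribution section speaks only of preliminary efficacy. All of that is right, and it limits the harm. It does not supply a comparator, and calling an effect preliminary does not make it estimable.

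A second reply is that a comparison may well have been intended. The session-order sentence and the rescue-proportion comparison both read as if a second group existed. This also stands. It is why the sponsor should be asked first, before the objective is rewritten.

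A third reply is that interpreting results with reference to rescue use, as the Data Analysis Plan requires, guards against over-reading. That rule is sensible, but it too lacks an analgesics-alone reference.

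A reader might also infer stronger points that the documents do not support:

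- *That the plan tests hypothesis b wrongly.* It states the hypothesis and specifies no test of it. The fault is an unanswerable hypothesis and the risk of misreading other tests.
- *That the documents say VR is used in every session.* This is an inference. They say VR runs throughout the hydrotherapy session, and they describe no session without it.
- *That the secondary question is explicitly about VR added to analgesics.* Only hypothesis b says so. On either reading the reference data are missing.
- *That 15 to 20 children is too few for this comparison.* Sample size is not the obstacle, because the contrast is missing at any number.

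**Conclusion.** The point holds. As written, hypothesis b and the secondary question cannot be answered: the plan provides zero analgesics-alone observations, so the effect of VR against standard treatment is not identifiable at any sample size. This conclusion rests on what the text describes and on no assumed SD or event rate; the FLACC figures above only illustrate it. It would change if the sponsor has a comparison cohort that the document does not mention.

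The consequence is limited to the secondary objective. It would be wrong to infer that the pilot as a whole is undermined, because the primary acceptability question and hypothesis a need no control group. Nor do the documents make progression to the larger trial depend on an efficacy result. The one decision they describe is whether to include the youngest children. The pilot can still usefully describe pain, anxiety, sedation and rescue use under VR plus analgesics. The inconsistency should be corrected before results are interpreted.

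**What to change.** 1. **Aim and Hypotheses.** First establish whether a comparison cohort was intended. If so, and if its data already exist, name the cohort and its source and confirm that it was measured on the same scales and at the same time points. If not, restate the secondary question and hypothesis b as descriptive, for example: to estimate pain, anxiety and sedation over time during hydrotherapy under VR plus analgesics, with 95% confidence intervals, to inform the larger trial.
2. **Contribution and Data Analysis Plan.** State that within-session changes are not evidence of VR efficacy against standard treatment, and limit the promise of preliminary efficacy accordingly.
3. **Data Analysis Plan, rescue medication and dichotomous variables.** Without a comparator, report rescue use as a single-group proportion with a confidence interval. Do not use the rescue comparison or the chi-square test as evidence for hypothesis b.

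Cost: this changes a stated objective, and the secondary objective becomes less ambitious. The descriptive route needs no extra patients or assessments. The cohort route depends on data that the documents do not describe.

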## **METHODS**

**Design**. Single-arm pilot study.

**Sample and Setting**. Participants will be recruited through convenience sampling upon admission to the surgical-trauma burn unit. The unit has a hydrotherapy room for inpatients and outpatients. Healthcare professionals usually present during hydrotherapy are: a burn wound care nurse, a nurse clinician from the pain clinic, an anesthetist, a physical therapist and an orderly. The size of the total desired sample is 15 to 20 participants depending on the recruitment rate since it is a pilot study. The study will take place in the hydrotherapy room of the CHU St. Justine, a large pediatric university teaching hospital in Montreal where the VR prototype is installed.

Eligibility criteria. Inclusion criteria: children from 2 months to 10 years old, with a burn injury, requiring a hydrotherapy session for burn wound care, and accompanied by a consenting parent/legal tutor who can understand, read, and write either French or English. Exclusion criteria: 1) Admitted to the intensive care Unit, 2) Neuro-cognitive disability that precludes children from interacting with the distraction intervention, 3) Unconscious or intubated during hydrotherapy session, 4) Suffering from epilepsy (considering the nature of the intervention), 5) Allergic to opioids or other analgesics used for standard pharmacological treatment.

**Intervention**: The child will visualize and interact with the virtual environment throughout the hydrotherapy session. VR prototype developed by the SAT will be used as the experimental intervention. It has a wide screen installed at the end of the hydrotherapy tank offering a 150-degree field view, on which appears a game allowing the child to have the immersive entertainment experience without the need to wear a helmet or 3D glasses. The child or a proxy, depending on age and burn site, will have the opportunity to interact with the game. The interactive component is not mandatory for the immersive and distractive experiences provided by the prototype. Video

games tailored to the child's age and injury, different from the commercially available ones, will be adapted to each age-group of children recruited with control over the speed of movement to avoid motion sickness.

**Measures**. Measures of baseline pain and anxiety will be recorded at T1, 30 minutes before the procedure, in the patient's room. Measures for procedural pain, anxiety and sedation level will be taken at: T2, before the procedure, upon arrival in the hydrotherapy room, T3, during the procedure (10 min after the beginning of the hydrotherapy session), T4, immediately after the procedure before leaving the hydrotherapy room and T5, 30 minutes after the procedure in the patient's room. The patient's comfort level will also be assessed during the procedure at T3. Finally, the acceptability of the intervention will be assessed through a questionnaire comprising items on the acceptability and satisfaction of the healthcare professionals at T4. The same measures will be recorded for each participant for up to three hydrotherapy sessions. The primary outcome will be the acceptability of the intervention. Comparisons will be made between pain and anxiety levels for the same order of session.

**A) Primary Outcome Measure**: Acceptability [Time Frame: T4, immediately after the procedure before leaving the hydrotherapy room]: To assess the acceptability including the satisfaction of healthcare professionals regarding the use of the VR prototype during the hydrotherapy session. Pre-tested tailored questionnaire including satisfaction and acceptability outcomes (tolerance, positive and negative aspects, secondary effects).

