# **FEASIBILITY**

The setting of the study is the main referral center for pediatric burns in Quebec. It receives nearly 60 admissions during the period when there is a higher incidence of burns (April to October) and almost 100 admissions per year. The investigators will be able to access the population for the study given the PI's affiliation to the research center of this setting. Moreover, stakeholders in the pain clinic and surgical-trauma unit are aware of the study, and participated in all stages of the prototype development.

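### Feasibility is in the primary question, but no count of children eligible, approached, enrolled or declined is planned, so the pilot cannot report uptake

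*Combined protocol and SAP*

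**What the plan says.** All places are in the combined protocol and SAP.

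- **Design and sampling (METHODS).** The study is a "Single-arm pilot study". On recruitment it says: "Participants will be recruited through convenience sampling upon admission to the surgical-trauma burn unit". It gives no rule for who is approached, in what order or by whom.
- **Entry (METHODS, eligibility criteria).** A child must be "accompanied by a consenting parent/legal tutor who can understand, read, and write either French or English". A family that declines therefore never enters the study data.
- **Sample size (METHODS).** "The size of the total desired sample is 15 to 20 participants depending on the recruitment rate since it is a pilot study". This is the only mention of the recruitment rate, and there it sets the final number. It is not listed as a result.
- **Primary outcome (METHODS, Measures and part A).** "Acceptability [Time Frame: T4, immediately after the procedure before leaving the hydrotherapy room". The text adds that "the acceptability of the intervention will be assessed through a questionnaire comprising items on the acceptability and satisfaction of the healthcare professionals at T4". On repeat sessions: "The same measures will be recorded for each participant for up to three hydrotherapy sessions".
- **Feasibility as a goal.** AIM names it in both the aim and the primary research question, and HYPOTHESES (item a) asserts it.
- **Analysis (DATA ANALYSIS PLAN).** Descriptive statistics cover sociodemographic and clinical variables, comfort and professionals' satisfaction. Screening, refusal and uptake are not mentioned.
- **Source population (FEASIBILITY).** "It receives nearly 60 admissions during the period when there is a higher incidence of burns (April to October"), and almost 100 in a year. The number of eligible children is not given.

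**The concern.** A pilot that asks whether an intervention is feasible is expected to say how many children could have received it, how many were offered it and how many took it up. This plan collects only the last of these counts, the children enrolled. A child who was never approached, or whose parents said no, leaves no trace in any planned measure or analysis.

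Three things are at stake.

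- **The feasibility answer.** Without a denominator there is no uptake figure to carry into the larger trial. Records of approaches and refusals are hard to rebuild reliably afterwards.
- **How far the acceptability result reaches.** The questionnaire is completed at T4, so it describes sessions in which VR was used with children who were selected and whose parents agreed. Hypothesis a speaks more broadly of young children with burn injuries.
- **The decision on infants.** POSSIBLE PITFALLS AND SOLUTIONS says the pilot will inform whether children aged 2 months to 2 years enter the larger trial. If they are approached less often, or their parents decline more often, nothing planned would show it.

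**Working it through.** **1. What the plan would count.** The 15 to 20 target has no alpha, power or precision behind it, so there is no figure to reproduce. The check is which terms of an uptake figure would be available.

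| Quantity | Planned? | Where |
|---|---|---|
| Eligible children | No | Not in the outcome lists or DATA ANALYSIS PLAN |
| Approached | No | As above |
| Declined, with reason | No | As above |
| Enrolled | Yes | METHODS, 15 to 20 |
| Acceptability in sessions with VR | Yes | METHODS, T4 questionnaire |

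Uptake = enrolled / approached, and approach rate = approached / eligible. Neither can be formed from the planned data.

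**2. What that leaves open.** The documents give no number of refusals, so the values below are assumptions across a range. The intervals are exact (Clopper-Pearson) 95% limits. For x enrolled of N approached, the lower limit is the 2.5% quantile of Beta(x, N−x+1) and the upper limit is the 97.5% quantile of Beta(x+1, N−x).

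| Assumed refusals | 15 enrolled | 20 enrolled |
|---|---|---|
| 0 | 15/15 = 100% (78% to 100%) | 20/20 = 100% (83% to 100%) |
| 2 | 15/17 = 88% (64% to 99%) | 20/22 = 91% (71% to 99%) |
| 5 | 15/20 = 75% (51% to 91%) | 20/25 = 80% (59% to 93%) |
| 10 | 15/25 = 60% (39% to 79%) | 20/30 = 67% (47% to 83%) |

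Every row in a column would produce the same planned dataset size. The intervals also show that uptake would be estimated only roughly, as is normal for a pilot.

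**3. Whether the direction of bias in acceptability can be derived.** Suppose, for argument, that acceptability were a yes/no result per child (the plan defines none). Let u be the share of approached families who take up VR, a the acceptability among users, and b what it would have been among non-users. Then

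A_all = u·a + (1−u)·b, so A_all − a = (1−u)(b−a).

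The difference is zero if u = 1 or b = a, negative if b < a and positive if b > a. With assumed a = 90% and u = 70%:

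- b = 0 gives 0.70 × 0.90 + 0.30 × 0 = 63%;
- b = 100% gives 0.70 × 0.90 + 0.30 × 1 = 93%.

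The documents give neither u nor b, so neither the size nor the sign follows.

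**4. Share of admissions.** 15/60 = 25% and 20/60 = 33% of April to October admissions; 15/100 = 15% and 20/100 = 20% of a year's. These shares do not measure the defect. They follow from the sample size, and consecutive enrolment stopping at 20 leaves the same 40 of 60, or 80 of 100, outside the sample. The denominators are also all admissions, not eligible children.

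**The case against.** The strongest reply has four parts.

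- **Convenience sampling is ordinary in a single-arm pilot of 15 to 20 children.** This stands, and convenience sampling alone is not called an error here. The gap arises because it is combined with no record of non-approach or refusal, in a study whose primary question includes feasibility.
- **The T4 questionnaire concerns healthcare professionals, who can rate the prototype only after using it.** This also stands. The timing suits that measure, and a family's refusal does not directly lower a professional's rating. It does not supply the missing uptake figure, and it does not extend the result to children who were never offered VR.
- **A screening log may be kept in practice.** Possibly: silence does not prove there is none. But the plan neither specifies one nor commits to reporting it.
- **Nothing shows that staff steer easier children into the study.** Correct. METHODS does not say who approaches families. FEASIBILITY says that pain clinic and surgical-trauma stakeholders took part in all stages of development, which is a reason to record approaches but not evidence of steering.

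A reader might infer that acceptability is overstated and that the bias favours hypothesis a. The documents do not support that. It would need uptake below 100% and less favourable views among those not included, and neither is given. A reader might also want to count each refusal as a rating of not acceptable. That would mix a consent decision with a professionals' questionnaire and could not be interpreted as either.

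**Conclusion.** The concern holds as a missing denominator. Feasibility is in the aim, the primary question and hypothesis a, and the plan as written cannot report uptake or show who was passed over. The acceptability result may come from a selected subset, but no bias of stated size or direction is established.

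The size of the gap is best expressed as what remains unknown: over the assumed range of 0 to 10 refusals, uptake could lie between 60% and 100% with 15 enrolled, or between 67% and 100% with 20. The conclusion rests on the outcome lists and DATA ANALYSIS PLAN being complete as published. If a log already exists, only the commitment to report it is missing. The change is worth making because it is cheap and lets the pilot answer its own question.

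**What to change.** **METHODS, Sample and Setting.** Replace convenience sampling with consecutive approach: every eligible admission is approached in order within a stated recruitment window, up to the planned 15 to 20 children. No extra staff are implied. Where a child cannot be approached, the reason is logged.

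**Screening log.** Record children eligible, approached, enrolled and declined, with reasons. Keep refusal of VR separate from refusal of research, since the two mean different things for the larger trial. Note at each session whether VR was used.

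**DATA ANALYSIS PLAN.** Report uptake (enrolled / approached) with an exact 95% CI as a feasibility result separate from the acceptability questionnaire, together with approached / eligible. Give both by age group, including 2 months to 2 years, as descriptive figures because the groups will be small. Limit the acceptability conclusion to sessions in which VR was used.

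**Cost.** A short log, a few lines of protocol text and no additional patients. Admissions run at about 100/12 = 8 per month before eligibility is applied, so the log stays small. The feasibility picture may look less favourable than one without a denominator.

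### Does repeated rating by the same few staff undermine the primary acceptability outcome?

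*Combined protocol and SAP*

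**What the plan says.** Under Methods, Measures, the protocol makes acceptability the primary outcome and states that "the acceptability of the intervention will be assessed through a questionnaire comprising items on the acceptability and satisfaction of the healthcare professionals at T4". The primary outcome entry gives the purpose: "To assess the acceptability including the satisfaction of healthcare professionals regarding the use of the VR prototype during the hydrotherapy session". The instrument is described as pre-tested and tailored, but it is not reproduced.

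The amount of data follows from two statements: "The size of the total desired sample is 15 to 20 participants depending on the recruitment rate since it is a pilot study", and "The same measures will be recorded for each participant for up to three hydrotherapy sessions".

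On who might rate, Methods, Sample and Setting lists the staff usually in the room: "a burn wound care nurse, a nurse clinician from the pain clinic, an anesthetist, a physical therapist and an orderly". There is one site: "The study will take place in the hydrotherapy room of the CHU St. Justine".

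The Aim includes "the satisfaction of the healthcare professionals regarding the use of the VR prototype for the relief of procedural pain and anxiety", and hypothesis (a) reads in part "VR distraction is a feasible and acceptable non-pharmacological method for procedural pain relief". The Data Analysis Plan assigns descriptive statistics to staff satisfaction. It does not mention acceptability separately.

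The text does not state who completes the T4 form, how many forms there are per session, the unit of summary, or whether raters are identified.

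**The concern.** A single room with five usual roles and up to 60 sessions suggests a small pool of raters, each contributing several forms. If so, a percentage of favourable forms or sessions shows how often the prototype was found acceptable, but not by how many people. Two or three professionals who attend most sessions could carry the result, and the same figure could equally come from broad agreement across the team.

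The worry has some weight because this is the primary outcome, because staff satisfaction is part of the stated aim, and because rater identity is hard to rebuild from unlabelled forms. The Background and Feasibility sections add that the surgical-trauma team and stakeholders from the pain clinic took part in developing the prototype, so some raters might not be neutral. What would be at stake is the wording of the main conclusion: whether the team accepts the device, or only its most frequent users.

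**Working it through.** The plan gives no figure for the number of raters or forms, so there is nothing of its own to reproduce. The check has three parts.

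**1. How likely is repeated rating?** Inputs from Methods: 15 to 20 children, one to three sessions each, five usual roles.

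- Sessions: 15 × 1 = 15 up to 20 × 3 = 60.
- Forms with one per session: 15 to 60. Forms with five per session: 15 × 5 = 75 up to 60 × 5 = 300.
- For nobody to rate twice, the number of different professionals must be at least the number of forms.

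The number of staff is not given. If it were 5, 10 or 20, then 60 forms would mean 12, 6 or 3 forms per person on average. At the other end, 15 forms from 20 staff need no repeats (15/20 = 0.75). Repetition is very probable but not certain.

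**2. How far could a per-form and a per-professional percentage differ?** Suppose a fraction *f* of the raters supplies a share *s* of the forms, with acceptance rate *a*, and the remaining raters have rate *b*.

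- Per form: *s·a* + (1 − *s*)·*b*
- Per professional: *f·a* + (1 − *f*)·*b*
- Gap: (*s* − *f*)(*a* − *b*)

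All values below are assumptions: 60 forms, 10 raters, three of them frequent (*f* = 0.30), and a yes/no rating.

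| Share of forms from the three | *a* | *b* | Per form | Per professional | Gap |
|---|---|---|---|---|---|
| 40/60 | 0.90 | 0.60 | (36 + 12)/60 = 80% | (2.7 + 4.2)/10 = 69% | +11 points |
| 40/60 | 0.60 | 0.90 | (24 + 18)/60 = 70% | (1.8 + 6.3)/10 = 81% | −11 points |
| 24/60 | 0.90 | 0.60 | 0.36 + 0.36 = 72% | 69% | +3 points |
| 18/60 | any | any | equal | equal | 0 |

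With a 40% share and a difference of 15 points, the gap is 0.10 × 0.15 = 1.5 points. It is also 0 whenever *a* = *b*. The 11-point case requires the three to complete 40/3 = 13.3 forms each against 20/7 = 2.9 for the others, a ratio of about 4.7, and also a 30-point difference in acceptance.

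**3. Does anything in the plan depend on the gap?**

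- *Unit.* The primary outcome entry ties the outcome to use during the session. A by-session description answers that directly, and repeated raters do not make it wrong.
- *Decision.* No acceptability threshold is set. The one later decision named, under Possible Pitfalls and Solutions, is whether infants enter the larger trial, and no rule there refers to staff ratings.
- *Precision.* No interval for acceptability is planned, so no standard error is understated by treating forms as independent.

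**The case for a change.** The strongest opposing case rests on timing. A unit of summary can be chosen at analysis, but an identifier that was never collected cannot be added afterwards. The Aim concerns professionals' satisfaction, so a reader will want to know how many professionals are meant. A pseudonymous code would cost almost nothing and require no extra patients.

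Part of this stands. The protocol is silent on respondent, forms per session and unit, and a by-session percentage should not be reported as a percentage of staff. The number of distinct raters would be useful context.

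The rest is weaker. The loss of information arises only if the questionnaire lacks an identifier. The form is not available, and a short protocol's silence on a form-level field is poor evidence that the field is missing. Coding also has a cost. In a team with five usual roles, a code together with a role could nearly identify a person. The study team would hold the key, yet according to the Background the researchers took part in the meetings that led to the prototype. That could reduce candour on the very outcome being measured. The suggestion that raters helped build the device is speculative, since the documents name groups and not raters.

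**Conclusion.** Repeated rating by a small staff is a fair inference, and the protocol could have said more about who completes the form. That is missing detail, not a fault in the analysis. Followed as written, the plan yields a usable description of acceptability by session, which matches the outcome definition. Under assumed inputs, the difference between counting forms and counting people ranges from 0 through 1.5 to 3 points for moderate imbalance, up to 11 points in either direction for a steep one. The direction is unknown, and no threshold or interval is affected. Analysts can handle this by naming the denominator, stating the number of distinct raters if the form allows it, and confining the conclusion to sessions if it does not.

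This conclusion rests on two readings. First, the session is the main unit. Second, acceptability is described and not tested, which the Data Analysis Plan states for staff satisfaction and which is inferred for any other acceptability items. If such items were dichotomous and were put through the plan's chi-square test, repeated raters would matter more. The text does not assign them there by name.
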